**Study Design**

This is a Randomized, Double-Blind, Placebo-Controlled Phase II interventional study that will test the efficacy of quintuple therapy, HAZDpaC (Hydroxychloroquine, Azithromycin, Zinc, Vitamin D, and Vitamin C), in the treatment of Subjects with COVID-19 infection, compared to Subjects given only the vitamins, zinc (to put both groups into nutritional balance), and 2 placebos to match the hydroxychloroquine and azithromycin.

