**Duration of Subject Participation (Study Visits)**

Subjects will be given the opportunity once diagnosis has been made via RT-PCR testing to participate. They may be recruited through the ProgenaBiome website, through a questionnaire. They may also be recruited through [www.clinicaltrials.gov](http://www.clinicaltrials.gov). Subjects may be referred by healthcare facilities. Subjects may also self-refer as well. All potential Subjects will be called during the recruitment process for screening assessments. The first step of this will be to obtain informed consent electronically, via the EDC. We will attempt to connect with these Subjects via Zoom/telemedicine. The validity of the test used to diagnose will be verified through medical records. (The diagnosis will be made by the Subject's evaluating physician or evaluation testing center, as part of the standard of care when infection is suspected). Following successful screening, Subjects will be randomized into the Arm 1 (treatment) or Arm 2 (placebo). At this time the associated treatment regimen will be prescribed and shipped to the Subject's home, along with home health equipment (MoMe Kardia II, thermometer, pulse oximeter and pregnancy test). Subjects will take azithromycin for 5 days, and hydroxychloroquine for 10 days, along with vitamin C, vitamin D, and zinc. Starting at Day 11 Subjects will discontinue hydroxychloroquine and reduce the doses of vitamin C, vitamin D, and zinc. The vitamin C, D, and zinc will be taken an additional 20 days at the reduced dose. Subjects will use the home EKG to transmit heart function information to the Study Team to be read by a board-certified cardiologist prior to dosing. The EKG will then be used daily for 10 days and results transmitted to the study team. Subjects will use a home pulse oximeter to monitor oxygen saturation and photographically report these values to the study team via the EDC. Subjects will track their symptoms using a daily diary (provided). Subjects will collect nasal or oropharyngeal swabs on Days 3, 5, 7, 14, and Month 1 and Month 3 for RT-PCR testing. Once Subjects have tested negative following treatment with HAZDpaC, Subjects will present to the clinic at 1, 2, and 3 months post-treatment for viral testing via RT-PCR. Alternatively, these visits may be conducted via videoconference and the subjects may collect these samples at home. At these visits blood will be drawn, a physical exam performed, and vital signs measured (optional). At the month 3 visit a pregnancy test will be given if applicable. Should Subject remain symptomatic at 2 weeks, or return to a positive state at any time during the trial they will be referred to their PCP by a phone call directly from the PI to the PCP. If at any time during the treatment phase or subsequent follow up Subject expresses and demonstrates a worsening or persistence of symptoms, they will be cared for according to standard of care or referred to their primary care provider, according to patient preference. The PI will discuss the case directly with that primary care provider. Subjects will continue to be followed for the remainder of the trial, and documentation of any additional treatments and Subject outcomes will be collected.

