## 15. Statistical analysis

The treated patients in this study will be compared to the placebo group. Measurements will include PCR test results, presence or absence of symptoms, and symptom severity. PCR results will be compared between the groups as positive or negative

In this study, the meaningful threshold will be calculated as mean change in clinical symptoms as recorded in the diary, from Day 1 through week 12. Each category in the diary will be assigned a number, 0 for None, 1 for Mild, 2 for Moderate and 3 for severe. Each category will be analyzed independently and they will be analyzed as a group. Ultimately, efficacy will be determined based upon reduction and/or progression of symptomatic days, reduction of symptom severity, as well as analysis of the subject's RT-PCR testing per protocol. These data will be compared to an existing database of de-identified Subject data.

The change of these measurements from the end to the baseline (post-pre) will be used as the primary outcome, for example,  $\mu_e = \mu_{e1} - \mu_{e0}$ , where  $\mu_{e1}$  and  $\mu_{e0}$  are the outcome of Subjects from the treatment group at the end and at baseline, respectively.

Categorical variables will be summarized by presenting the number (n) and percent (%) of subjects in each category. All Statistical tests for the analysis will be performed using the  $p < 0.05$  level of significance. All confidence intervals will be one-sided

Sample size was calculated as follows:

$$n = \frac{\log \beta}{\log \rho}$$

Where  $\beta = \text{the probability of a Type II error}$

$\rho = \text{the proportion of the population NOT affected}$

The proportion of the population affected by COVID-19 is 0.005 percent, thus 0.995 percent aren't affected

The probability of a type II error is 0.05

Thus:

$$n = \frac{\log 0.050}{\log 0.995}$$

$$n = 597.647$$

A sample size of 600 will be used

Additional details can be found in the Statistical Analysis Plan that will be developed prior to database lock.

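### Section 15 adds a comparison with an undescribed external database and does not say how it ranks against the randomised placebo comparison

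*Combined protocol and SAP*

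**What the plan says.** The synopsis (Study Design) describes the trial this way: "This is a Randomized, Double-Blind, Placebo-Controlled Phase II interventional study that will test the efficacy of quintuple therapy". Both arms receive vitamin C, vitamin D and zinc, and Arm 2 receives two placebos in place of the two study drugs.

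Section 15 (Statistical analysis) opens with the concurrent comparison: "The treated patients in this study will be compared to the placebo group". It then says what the efficacy judgement rests on: "Ultimately, efficacy will be determined based upon reduction and/or progression of symptomatic days, reduction of symptom severity", together with the RT-PCR results. The next sentence is "These data will be compared to an existing database of de-identified Subject data".

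That is the only mention of the external database. The documents do not give its source, calendar period, size, eligibility, basis of diagnosis, background treatment or outcome definitions. They do not say which arm or arms would be compared with it, whether a test would be done, how differences in case mix would be handled, or whether the result is primary, supportive or descriptive. Section 15 leaves further detail to a statistical analysis plan to be written before database lock. The documents supplied contain no such plan.

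**The concern.** Two comparators are named for the same efficacy measures and nothing ranks them. The randomised, blinded one protects against confounding and against differences in how outcomes are collected. The other has neither protection.

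This trial recruits partly by self-referral and through a website. It accepts diagnosis by clinical presentation as well as by test, applies a long list of health-based exclusions, collects swabs at home on fixed days and scores symptoms from a self-completed diary. Both arms take the supplements. Subjects in an outside database may differ in diagnosis route, severity, calendar time, testing schedule or supplement use. Any such difference would be mixed with the drug effect in the external comparison, and could favour the drug or count against it.

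What is at stake is how the result can be read. If the two comparisons disagree, the protocol does not say which one determines efficacy.

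**Working it through.** **1. Order of the text.** In section 15 the placebo comparison comes first, the list of efficacy measures later, and the database sentence directly after that list. The opening words of the database sentence most naturally refer back to those measures, so the external comparison concerns efficacy data. No sentence limits or ranks it.

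**2. The plan's own figure.** The only design calculation is the sample size: log(0.05)/log(0.995) = 597.647, taken as 600. It reproduces. The formula contains no comparator, effect size or significance level, so it says nothing about either comparison and is unaffected by this point.

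**3. Illustration of what case mix can do.** The plan gives no figures for the external comparison, so these inputs are assumptions unless noted:
- Treated subjects: 300, which is half of the plan's 600. The allocation ratio is not stated; 1:1 is assumed.
- External subjects: N = 300 to 10,000.
- Outcome: one yes/no recovery proportion, about 50%.
- No true drug effect, and a case-mix difference b of 3, 5 or 10 percentage points.
- Two-sided test at 0.05. The 0.05 is the plan's; the sidedness of tests is not stated.

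SE = sqrt(0.25 × (1/300 + 1/N))

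P(p<0.05) = Φ(b/SE − 1.96) + Φ(−b/SE − 1.96)

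Worked case, N = 3000: SE = sqrt(0.25 × 0.0036667) = 0.0303. For b = 0.05, b/SE = 1.651 and Φ(−0.309) = 38%. For b = 0.10, b/SE = 3.303 and Φ(1.343) = 91%. The second term is negligible in both.

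| External N | SE | b = 0 | b = 3 points | b = 5 points | b = 10 points |
|---|---|---|---|---|---|
| 300 | 0.0408 | 5% | 11% | 23% | 69% |
| 1000 | 0.0329 | 5% | 15% | 33% | 86% |
| 3000 | 0.0303 | 5% | 17% | 38% | 91% |
| 10,000 | 0.0293 | 5% | 18% | 40% | 93% |

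A version with a pooled null and an unpooled alternative standard error gives nearly the same values (23% and 69% at N = 300; 33% and 86% at N = 1000).

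The randomised comparison has no systematic case-mix difference between arms, so it keeps its nominal 5%.

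**4. Sidedness.** Section 15 says "All confidence intervals will be one-sided". If tests were also one-sided at 0.05, 1.645 replaces 1.96. A bias favouring treatment would then give 34-52% at 5 points and 79-96% at 10 points over the same range of N. A bias against treatment would push the rate of favourable findings below 5%.

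**The case against.** The strongest reply is that the text does not make the database decisive. It says only that data will be compared with it and names no test, arm, endpoint or decision rule. The placebo comparison is stated first and the whole design is randomised and blinded, so a purely contextual comparison is an equally available reading. The later analysis plan might also settle the matter.

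Much of this stands, and it rules out three stronger readings:
- A reader might infer that the database replaces the placebo arm, or that a favourable external result may override a null randomised one. No sentence says so; the role is left undefined.
- A reader might infer that the external subjects do differ from trial subjects in the ways listed above. The database is undescribed, so the documents support only that they may differ.
- A reader might infer that small case-mix differences are bound to produce significance. The illustration does not show this: at 5 points significance is missed 60-77% of the time, and at 3 points 82-89%.

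It is also fair that the illustration uses a single binary outcome, whereas the stated primary endpoint is days to recovery by RT-PCR and section 15 also calls a post-minus-pre change the primary outcome. The percentages therefore show a principle and do not estimate the bias in this trial.

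The reply does not remove the gap. A contextual reading is available, but so is one in which the external comparison supports an efficacy claim. Deferral to a plan due only before database lock leaves the choice of database and its role open until late in the trial. The rank of the two comparators belongs in the protocol.

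**Conclusion.** The point holds as one of undefined role and undescribed source. As written, section 15 allows a non-randomised, possibly confounded comparison to enter the efficacy conclusion although a randomised placebo arm exists. Confidence is high that the role and source are missing. How much the comparison would distort the conclusion cannot be judged from the documents, because size, direction and intended use are all unknown.

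The illustrative rates of nominal significance without any drug effect (23-40% at a 5-point difference, 69-93% at 10 points) depend wholly on the assumed 300 treated subjects, 50% recovery, binary outcome, two-sided 0.05 test and 300 to 10,000 external subjects. The change should be made. It is more than a request for detail, because it fixes which comparison decides efficacy.

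**What to change.** In section 15, state that efficacy is determined only by the randomised comparison of Arm 1 with Arm 2. Then either:
- delete the database sentence; or
- keep the comparison, label it descriptive or supportive, and state that it has no role in the efficacy conclusion. If it is kept as supportive, pre-specify the database source, calendar period, eligibility, endpoint definitions and method of adjustment.

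The change takes a sentence or two, plus a short specification if a supportive analysis is wanted. The sample size, visits and data collection are untouched. The only loss is any confirmatory use of the database.

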### Exclusion Criteria

1. Refusal to provide informed consent
2. Pregnant or breastfeeding women
3. Diarrhea prior to infection
4. Negative test for COVID-19 by RT-PCR or rapid antigen test at screening
5. Any comorbidities which, in the opinion of the investigator, constitute health risk for the subject
6. Any contraindications for treatment with hydroxychloroquine
  - a. Hypoglycemic
  - b. Known G6PD deficiency
  - c. Porphyria
  - d. Anemia
  - e. Neutropenia
  - f. Alcoholism
  - g. Myasthenia gravis
  - h. Skeletal muscle disorders
  - i. Maculopathy
  - j. Changes in visual field
  - k. Liver disease
  - l. Psoriasis
  - m. History of QT interval >500msec
  - n. History of torsades de pointes
7. Anemia from pyruvate kinase and G6PD deficiencies
8. Abnormal EKG with QT prolongation acquired or from birth
9. Allergies to 4-Aminoquinolines
10. History of jaundice or high fevers prior to developing COVID-19
11. Treatment with any of the medications listed in Appendix II
12. Treatment with any other drug not listed that affects the QT interval
13. Treatment with any anti-epileptics

ProgenaBiome, LLC Protocol PRG-044	21 July2020
Number of Subjects	
Subjects will be enrolled to ensure that at least 600 complete the study. It is anticipated that screening of 1200 Subjects will be required to achieve this.	
Specimen Requirements:	
NP swabs (synthetic swab on plastic shaft) placed into 2-3mL of viral transport media. 1 mL of blood in an EDTA and 2 mL of serum in two serum separator tubes spun down	
Study Duration	
Screening of 1200 Subjects and enrollment of 600 Subjects is expected to take 3 months	

Primary Study Objective	Study Endpoints
The rate of recovery from COVID-19 in Subjects using Quintuple Therapy	Number of days from COVID-19 diagnosis to recovery via RT-PCR
Reduction or Progression of Symptomatic Days	Reduction and/or progression of symptomatic days, reduction of symptom severity
Secondary Objectives	Study Endpoints
Assess the safety and Tolerability of Quintuple Therapy	Assess the symptom response to study therapy as measured by the survey in the EDC
	EKG response, oxygen saturation, and vital signs at baseline, 2 weeks, 1 month, and two months
	Assess Adverse Events and Serious Adverse Events due to Quintuple Therapy

- a. Adverse event monitoring will be conducted for 12 weeks
- b. Serious adverse event monitoring will be conducted for 12 weeks

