## 2. Trial Objectives

Primary Study Objective	Study Endpoints
The rate of recovery of mild or moderate COVID-19 in Subjects using Quintuple Therapy	Number of Days Recovery from COVID-19 diagnosis to Recover via RT-PCR
Secondary Objectives	Study Endpoints
Assess the safety of Quintuple Therapy	Assess the symptom response to study therapy as measured by the survey in the EDC
	EKG response, oxygen saturation, and vital signs at baseline, 2 weeks, 1 month, and two months
Assess Tolerability of Quintuple Therapy	Assess Adverse Events and Serious Adverse Events due to Quintuple Therapy

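### Section 15 makes an end-minus-baseline change with no stated end day the primary outcome, specifies no analysis of the declared primary endpoint (days to RT-PCR recovery), and sets a diary window to week 12 although the diary stops at Day 30

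*Combined protocol and SAP*

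**What the plan says.** Three parts of the protocol describe the primary outcome.

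- **Synopsis, objectives table.** The first primary row has the endpoint "Number of days from COVID-19 diagnosis to recovery via RT-PCR". A second primary row adds "Reduction and/or progression of symptomatic days, reduction of symptom severity".
- **Section 2, Trial Objectives.** The only primary row is "Number of Days Recovery from COVID-19 diagnosis to Recover via RT-PCR". Symptomatic days and severity are not primary here.
- **Section 15, Statistical analysis.** The measurements listed are PCR result, presence of symptoms and symptom severity. On PCR: "PCR results will be compared between the groups as positive or negative". On efficacy: "Ultimately, efficacy will be determined based upon reduction and/or progression of symptomatic days, reduction of symptom severity", to which the sentence adds an analysis of the protocol's RT-PCR testing without naming a method. Then: "The change of these measurements from the end to the baseline (post-pre) will be used as the primary outcome".

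Section 15 sets its meaningful threshold on the "mean change in clinical symptoms as recorded in the diary, from Day 1 through week 12". It closes by deferring detail: "Additional details can be found in the Statistical Analysis Plan that will be developed prior to database lock".

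On data collection, Section 3 and the Section 6 schedule have the diary completed from Day 1 through the Day 15-30 block, with none at Months 1, 2 or 3. Swabs are scheduled on Days 3, 5, 7 and 14 and at Months 1 and 3.

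**The concern.** Days to recovery is a time-to-event quantity. A difference between a baseline value and one later value is a different outcome and answers a different question. With PCR coded positive or negative, it records whether a subject has cleared by the end day, not how fast. The stated objective is the rate of recovery. A comparison at one fixed day addresses that inefficiently, and at a late day, when most subjects in both arms have cleared, it may hardly address it at all.

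Because the end has no day, the result depends on a choice the protocol does not make. The only nearby time is week 12, in the diary sentence. If that is the end, the symptom part of the primary outcome has no data. Anyone following Section 15 literally would leave the declared endpoint unanalysed and could not compute the symptom window it sets.

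**Working it through.** **1. The plan's own figure.** Section 15 gives n = log(0.05)/log(0.995) = 597.647, used as 600. This reproduces. The formula contains no treatment effect, significance level, event count or follow-up time, so it does not show which primary outcome was intended.

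**2. Diary coverage (from the documents alone).** Week 12 is 12 × 7 = 84 days. The diary ends at Day 30. 84 − 30 = 54 days without a diary; 54/84 = 64%. PCR has no such gap, because a Month 3 swab is scheduled.

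**3. How much the end day matters (illustration only).** The documents give no recovery curve, effect size or score SD. Assumed:

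- exponential time to recovery, control median 5, 7, 10, 14 or 20 days;
- treated median × 0.7 (30% cut, rate ratio 1/0.7 = 1.43) or × 0.8 (rate ratio 1/0.8 = 1.25);
- 300 per arm, two-sided 0.05, same effect on symptoms and PCR;
- baseline severity B with mean 1.5 and SD 0.4 or 0.8.

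The fraction not recovered at day t is p = 0.5^(t/median). For positive/negative PCR, z = |p_C − p_T| / √[(p_C(1−p_C) + p_T(1−p_T))/300] and power = Φ(z − 1.96) + Φ(−z − 1.96).

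Example, control median 10, treated median 7:

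- Day 14: p_C = 0.379, p_T = 0.250; SE = √[(0.2353 + 0.1875)/300] = 0.0375; z = 3.43; power 93%.
- Day 84: p_C = 0.0030, p_T = 0.0002; SE = 0.0033; z = 0.83; power 13%.

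For the severity change score (a recovered subject falls from B to 0, others do not change), the mean is −1.5(1−p) and the variance is (2.25 + SD²)(1−p) − [1.5(1−p)]². Same example, SD 0.8, Day 14: means −0.932 and −1.125; variances 0.927 and 0.902; SE = √(1.829/300) = 0.0781; z = 2.48; power 70%.

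Time to recovery was assessed with a log-rank test on grouped swab days 3, 5, 7, 14, 30 and 90, with no missed swabs and 4,000 simulations.

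Power (%) by control median, 30% cut:

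| Analysis | 5 d | 7 d | 10 d | 14 d | 20 d |
|---|---|---|---|---|---|
| PCR +/−, Day 14 | 91 | 94 | 93 | 89 | 82 |
| PCR +/−, Day 30 | 39 | 72 | 89 | 94 | 93 |
| PCR +/−, Day 84 | 5 | 6 | 13 | 39 | 74 |
| Severity change, Day 14, SD 0.8 | 39 | 60 | 70 | 70 | 64 |
| Severity change, Day 14, SD 0.4 | 71 | 85 | 87 | 84 | 77 |
| Severity change, Day 30, SD 0.8 | 6 | 13 | 34 | 57 | 69 |
| Severity change, Day 30, SD 0.4 | 9 | 30 | 66 | 83 | 87 |
| Time to recovery | 98 | 98 | 98 | 98 | 97 |

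Power (%) at rate ratio 1.25:

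| Analysis | 5 d | 7 d | 10 d | 14 d | 20 d |
|---|---|---|---|---|---|
| PCR +/−, Day 14 | 56 | 59 | 56 | 50 | 42 |
| PCR +/−, Day 30 | 23 | 41 | 55 | 59 | 57 |
| PCR +/−, Day 84 | 5 | 6 | 10 | 23 | 42 |
| Time to recovery | 73 | 73 | 71 | 70 | 68 |

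If the Month 3 swab is taken as Day 90, the late PCR comparison has 5-68% (30% cut) or 5-38% (rate ratio 1.25).

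**The case against.** The strongest reply is that Section 15 is less far from the synopsis than it looks. Its efficacy sentence covers symptomatic days, severity and RT-PCR, which matches the two primary rows there, and its reference to RT-PCR testing per protocol could be read as meaning the serial swabs. That reading is fair, but it names no method and no days-to-recovery variable. The sentence defining the primary outcome still says post minus pre.

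Second, week 12 belongs to the diary threshold, not to the primary-outcome sentence, and 64% is calendar time rather than information. Under the model above only 2% (median 5: 0.5^6) to 35% (median 20: 0.5^1.5) of controls are still unrecovered at Day 30. Both points stand. Change within Days 1-30 can be computed, but the window as written cannot.

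Third, the power figures rest on assumptions. The time-to-recovery benchmark takes no missed swabs and every subject positive at baseline. A Day 14 PCR comparison is informative, and part of the severity score's low power comes from not adjusting for baseline. Adjusting for the Day 1 score lifts its Day 14 power (SD 0.8, 30% cut) from 39-70% to roughly 72-87%. This is accepted: the figures show dependence on the end day and do not measure the defect.

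Finally, the trial is double-blind and an SAP is promised before database lock. It could supply an end day and an estimator without knowledge of the arms. It would not remove the conflict between the synopsis, Section 2 and Section 15.

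**Conclusion.** The concern holds and must be fixed. This is more than missing detail: a stated rule puts a different outcome in place of the declared primary endpoint, and a second rule sets a window that the data collection cannot fill. Both conclusions come from the text alone, as does the 54 of 84 days (64%) without a diary.

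The cost in power depends on the assumed recovery curve. For a 30% shorter median, a Day 14 PCR comparison loses moderately against time to recovery (82-94% against about 97-98%). A week 12 comparison is weak over most of the range (5-74%). At rate ratio 1.25 the corresponding figures are 42-59%, about 68-73% and 5-42%.

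**What to change.** - Name the same single primary outcome in the synopsis, Section 2 and Section 15: time to RT-PCR recovery, as Section 2 already has it. Make symptomatic days and severity secondary, or state how they share the primary claim. That choice is the sponsor's.
- Compare the arms with a time-to-event method that allows for the scheduled swab days, for example an interval-censored or discrete-time analysis.
- Delete the post-minus-pre definition as primary.
- Limit the diary analysis to Days 1-30, compared between arms and adjusted for the Day 1 score.
- State the time origin, what counts as recovery (for example, whether one negative swab is enough), and how subjects with no positive baseline RT-PCR are handled. The last is needed because inclusion criterion 4 admits clinical or antigen diagnosis and the first study swab is on Day 3. The synopsis text on study participation speaks of RT-PCR diagnosis, so these passages should be reconciled too. These are supporting points on which the main finding does not rest.

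The cost is rewording, with no new visits, swabs or procedures. The downside is that subjects without a positive baseline RT-PCR may contribute little to the primary analysis, and their number is not given. If the sponsor chose to leave them out and they were half the sample (150 per arm left), illustrative power for time to recovery would fall to about 79-83% for a 30% cut, or 40-44% at rate ratio 1.25.

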- Temperature

- d. Subject will take prescribed regimen

Drug	AM Dose	PM Dose
Hydroxychloroquine (or Placebo)	200mg	200mg
Vitamin C	1500mg	1500mg
Vitamin D	1500IU	1500IU
Zinc	25mg	25mg

- o Day 11-Day 13

- a. Subject will complete AM/PM diaries

- b. Subject will take prescribed regimen

Drug	AM Dose	PM Dose
Vitamin C	750mg	750mg
Vitamin D	750IU	750IU
Zinc	12.5mg	12.5mg

- o Day 14

- a. Subject will be called

- Remind them to collect nasal or oropharyngeal swab
- Ask about AE/SAE
- Symptom resolution or progression
- Answer any questions the Subject may have

- b. Subject will collect nasal or oropharyngeal swab

- c. Subject will complete AM/PM diaries

- d. Subject will take prescribed regimen

Drug	AM Dose	PM Dose
Vitamin C	750mg	750mg

Vitamin D	750IU	750IU
Zinc	12.5mg	12.5mg

- Day 15-30
  - a. Subject will complete AM/PM diaries
  - b. Subject will take prescribed regimen

Drug	AM Dose	PM Dose
Vitamin C	750mg	750mg
Vitamin D	750IU	750IU
Zinc	12.5mg	12.5mg

- Follow-Up Period (These visits can be conducted via videoconference or in person)
  - Month 1 (outpatient only AFTER negative test)
    - a. Vital signs (BP, HR, RR, oxygen saturation, temperature)
    - b. Assessment for AE and SAE
    - c. EKG (Optional)
    - d. Physical exam (Optional)
    - e. Blood draw for CBC/Complete metabolic panel/C-Reactive Protein/Blood hydroxychloroquine levels/SARS-CoV Antibody test (All optional)
      - Blood HQ levels will remain blinded from all but unblinded coordinator
    - f. Update list of prior and concomitant medications
    - g. Study team will collect nasal or oropharyngeal swab (If patient elects to refrain from this in-person visit they will collect this at home)
  - Month 2 (outpatient)
    - a. Vital signs (BP, HR, RR, oxygen saturation, temperature)
    - b. Assessment for AE and SAE
    - c. EKG (Optional)
    - d. Physical exam (Optional)
    - e. Blood draw for CBC/Complete metabolic panel/C-Reactive Protein (Optional)
    - f. Update list of prior and concomitant medications
  - Month 3 (outpatient)
    - a. Vital signs (BP, HR, RR, oxygen saturation, temperature)
    - b. Assessment for AE and SAE
    - c. EKG (Optional)
    - d. Physical exam (Optional)
    - e. Blood draw for CBC/Complete metabolic panel/C-Reactive Protein (Optional)
    - f. Update list of prior and concomitant medications

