## **6. Schedule of Events**

On next page

Assessment	Screening (Day -7 to Day 1)	Day 1	Day 2	Day 3	Day 4	Day 5	Day 6	Day 7	Day 8	Day 9	Day 10	Day 11	Day 12	Day 13	Day 14	Days 15-30	Month 1 (± 4 days)	Month 2 (± 4 days)	Month 3 (± 4 days)
Informed Consent & Demographics	X																		
Make list of prior and concomitant medications	X			X				X			X				X		X	X	X
Confirmation of COVID-19 diagnosis	X																		
Review of Medical Records	X																		
Prescription of Antimicrobials a	X																		
Provide home health equipment b	X																		
Pregnancy test c		X																	X
Call Subject at home d		X		X		X		X			X				X				
Vitals at home e		X	X	X	X	X	X	X	X	X	X								
Subject will complete AM/PM diary		X	X	X	X	X	X	X	X	X	X	X	X	X	X	X			
Hydroxychloroquine 200mg BID (or placebo)		X	X	X	X	X	X	X	X	X	X								
Azithromycin 500mg (2 tablets) once daily (or placebo)		X																	
Azithromycin 250mg (1 tablet) once daily (or placebo)			X	X	X	X													
Vitamin C 3000mg (2 capsules) twice a day		X	X	X	X	X	X	X	X	X	X								
Vitamin D 3000IU (2 capsules) twice a day		X	X	X	X	X	X	X	X	X	X								
Zinc 50mg (2 capsules) twice a day		X	X	X	X	X	X	X	X	X	X								
Vitamin C 1500mg (1 capsule) twice a day												X	X	X	X	X			
Vitamin D 1500IU (1 capsule) twice a day												X	X	X	X	X			
Zinc 25mg (1 capsule) twice a day												X	X	X	X	X			
Ask about AE and SAE				X				X			X				X		X	X	X
Vitals in-clinic f																	X	X	X
Physical exam																	X	X	X
EKG in-clinic																	X	X	X
Swabs for RT-PCR				X		X		X							X		X		X
Bloodwork g																	X	X	X
Review list of prior and concomitant medications		X	X	X	X	X	X	X	X	X	X	X	X	X	X	X	X	X	X
SARS-CoV-2 Antibody test (optional, +4 days)																	X		
Blood Hydroxychloroquine level (optional)																	X		

- a. To include hydroxychloroquine 200mg tablets (#20), azithromycin 250mg tablets (#6), vitamin C 750mg capsules (#80), vitamin D 750IU capsules (#80), zinc 12.5mg capsules (#80)
- b. To include EKG (worn continuously), pulse oximeter, and thermometer
- c. If Subject is a woman of childbearing potential
- d. To remind them to collect swabs for RT-PCT, ask about AE/SAE, ask about symptoms, and answer any questions

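### Section 15's end-minus-baseline primary outcome conflicts with the listed symptomatic-days endpoint, leaves the end day undefined, and cannot show faster symptom recovery if that day is late

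*Combined protocol and SAP*

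**What the plan says.** Section 15 states: "The change of these measurements from the end to the baseline (post-pre) will be used as the primary outcome". Its worked formula subtracts a baseline term from an end term and has no others. The symptom scale is defined there ("Each category in the diary will be assigned a number, 0 for None, 1 for Mild, 2 for Moderate and 3 for severe"), and the period of interest is described as "mean change in clinical symptoms as recorded in the diary, from Day 1 through week 12". No day is named as the end.

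The same section also says that "efficacy will be determined based upon reduction and/or progression of symptomatic days, reduction of symptom severity", together with RT-PCR results, will decide efficacy.

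The Synopsis table of objectives and endpoints has two rows under the primary objective. The first is "The rate of recovery from COVID-19 in Subjects using Quintuple Therapy", measured by "Number of days from COVID-19 diagnosis to recovery via RT-PCR". The second is symptomatic days and symptom severity. Section 2 lists only the RT-PCR endpoint as primary.

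The Schedule of Events (Section 6) has the row "Subject will complete AM/PM diary" marked from Day 1 through Days 15-30 and blank at Months 1, 2 and 3. Section 3 gives the same twice-daily diary for the same days.

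Section 15 names no time-to-event or repeated-measures method and leaves further detail to an analysis plan to be written before database lock.

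**The concern.** One sentence declares a two-point change to be the primary outcome. Two other places make the count of symptomatic days primary or decisive. These are different quantities: the change asks how ill subjects are at one later moment, while symptomatic days ask how long they were ill. An analyst following Section 15 literally would test the first. An analyst following the Synopsis would test the second.

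The difference matters because outpatients with mild or moderate COVID-19 can be expected mostly to recover in either arm. At a late end day the change measures little more than how severe each subject was at baseline. A treatment that shortened symptoms by days could then show no difference on the declared primary symptom outcome. With no rule of precedence, the choice between the two could also be made after results are known.

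**Working it through.** **1. The plan's own figure.** Section 15 gives n = log(0.050)/log(0.995) = 597.647, rounded to 600. This reproduces. It contains no effect size, standard deviation or between-arm comparison, so the plan states no power for any symptom outcome against which to check.

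**2. Diary entries against the outcome.** Thirty days × 2 entries = 60 scheduled entries per subject. The change uses two time points. Week 12 is Day 84, which is 54 days after the last scheduled diary day, so a week-12 end has no scheduled diary value.

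**3. Why a late end day loses the signal.** Let B be the baseline score and E the end score, so change = E − B. The between-arm difference in mean change is (mean E, active − mean E, control) − (mean B, active − mean B, control). Randomisation makes the second bracket zero in expectation. If nearly all subjects in both arms have E = 0, the first bracket is near zero too, whatever happened in between. This step needs no assumption about recovery times beyond near-complete recovery by the end day.

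**4. Size, with every input assumed.** The documents give no recovery times, spread, effect or allocation ratio. Assumed: 300 per arm, two-sided 5%, baseline mean score 1.5 (SD 0.5), linear decline to 0, log-normal duration with log-SD 0.7, and medians of 12 v 9.6, 10 v 8 or 8 v 6.4 days (20% shorter on active).

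Hand check for 12 v 9.6 at Day 30:
- Still symptomatic on control: P(Z > ln(30/12)/0.7) = P(Z > 1.309) = 9.5%. On active: P(Z > ln(30/9.6)/0.7) = P(Z > 1.628) = 5.2%.
- Mean residual score = 1.5 × [P(Z > z) − (30/median) × exp(0.7²/2) × P(Z > z + 0.7)]. This gives 0.036 on control and 0.018 on active, a difference of 0.018.
- Standard error, taking the SD of the change as about the baseline SD: 0.5 × √(2/300) = 0.041.
- Ratio 0.018/0.041 = about 0.45, so power is about Φ(0.45 − 1.96) + Φ(−0.45 − 1.96) = about 7%.

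Simulated power over the three pairs of medians:

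| Outcome | Power |
|---|---|
| Change to Day 7 | 76-85% |
| Change to Day 14 | 19-46% |
| Change to Day 30 | 5-8% |
| Change to week 12 | 5-6% |
| Mean daily score | 85-87% |
| Symptomatic days to Day 30 | about 96% |

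Repeat runs move these by a few points.

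**5. Sensitivity to spread.** With log-SD 1.0 (12 v 9.6 days), more subjects are still ill at Day 30. The contrast narrows to about 15% for the Day 30 change, 73% for symptomatic days and 61-62% for the mean score.

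**6. A different model.** Weibull recovery times (shape 1 or 2), graded baseline 1-3, and medians of 7 v 5, 10 v 7, 10 v 8 and 14 v 10 gave 16-98% for the change at Day 14, 4-47% at Day 30 and 5-7% at week 12, against 70-100% for symptomatic days. For 10 v 7, mean symptomatic days differed by about 3.0-3.2, while the week-12 change differed by about 0.00 points.

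**The case against.** A reader might infer three stronger things, and the documents support none of them.

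- **That the plan uses only two diary points and discards the rest.** It does not say so. Symptomatic days, listed in the Synopsis and again in Section 15, can be counted only from the daily entries. The defect is an unreconciled pair of definitions.
- **That the trial cannot detect faster recovery, so a null result is to be expected even if treatment works.** The days-to-recovery endpoint is by RT-PCR, from swabs on Days 3, 5, 7 and 14 and at Months 1 and 3. It does not depend on the diary change.
- **That the loss is independent of which day is called the end.** It is not. In the same model the change has 76-85% power at Day 7. With longer assumed medians (20 v 16 days), the Day 14 change has 80%, above the 76% of the mean score over Days 1-14. An early end day removes most of the problem.

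It is also fair to say that all the power figures rest on assumed inputs, that Section 15 does not state whether tests are one- or two-sided, and that a later analysis plan is promised.

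What survives is that Section 15's wording points to a late end (week 12, or Day 30 as the last diary day), which is where the change fails. Baseline adjustment helps but does not cure it: the adjusted Day 30 analysis had 21-43% power against 91-94% for the adjusted Day 1-30 mean score. A later plan can add detail, but it does not by itself reconcile a primary outcome already declared in the protocol.

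**Conclusion.** The point holds in a limited form. Section 15 declares a primary outcome that conflicts with the symptomatic-days endpoint under the primary objective, and it leaves the end day undefined with a stated horizon beyond the last diary entry. If the end is Day 30 or week 12 and nearly all subjects have recovered, the outcome has power close to the 5% error rate for faster symptom recovery, while symptomatic days have about 96% under the main assumptions and 73% with wider spread. That recovery is near complete by then is itself an assumption: in the main scenarios 91-99% of subjects score 0 at Day 30. If many remain symptomatic, or the end is early, the change keeps useful power. The conclusion concerns the symptom outcome only and does not reach the RT-PCR endpoint.

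**What to change.** In Section 15:

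- Replace the end-minus-baseline change as the primary symptom outcome with the number of symptomatic days already listed in the Synopsis, counted from all diary entries over a fixed window within the diary period (Days 1-30) and compared between the randomised arms.
- Use the mean daily total diary score over the same window as the severity measure.
- Keep end-minus-baseline as a supportive summary only, with a named end day within Days 1-30.
- State how the symptom outcome ranks against RT-PCR days to recovery, and make the Synopsis and Section 2 agree.

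The diary data are already scheduled, so the cost is protocol and analysis-plan wording. The small downside is that the effect is expressed in days or average-score units rather than as a simple before-after change.
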